5. STUDY PERIODS, TREATMENT REGIMENS, AND POPULATIONS FOR ANALYSIS

5.1. Study Periods for Analyses

Study periods are defined in Table 2.

Table 2: Definition of Study Periods for Analysis

Period	Definition
Baseline / Screening	From the day of Informed consent form (ICF) signature (up to 28 days before first dose) to the day and time of the first dose of study drug.
On-treatment	From the date of first dose of study drug through 30 days after the last dose of study drug. Unless otherwise specified, the on-treatment period will be the basis for the summaries of safety.

5.2. Treatment Groups/Cohorts

There are 4 groups (cohorts) in this study as described in Section 4.1. 20mg QD of TAS-120 will be administered to the patients in Cohort 1, 2 and 3. In Cohort 4, TAS-120 will be administered at a dose of 20 or 16 mg QD, depending on the DLT observations in the safety lead-in phase. Fulvestrant 500 mg will also be administered to patients in Cohort 4 on Days 1 and 15 of cycle 1, then Day 1 every subsequent cycle thereafter.

This is an open-label, non-randomized study. Blinding/unblinding is not applicable.

5.3. Populations for Analysis

- All Enrolled Population: All patients enrolled in this study
- All Treated Population: All enrolled patients who received at least 1 dose of TAS-120
- **DLT Evaluable Set:** All patients in the All Treated Population in Cohort 4, excluding those for whom the cumulative dose of TAS-120 was <75% of planned TAS-120 dose or the cumulative dose of fulvestrant was <100% of planned fulvestrant dose for reasons other than DLTs in Cycle 1, or who received prohibited concomitant medications or therapies
- Response Evaluable Set: All patients in the All Treated Population who meet Inclusion Criterion #4 (section 4.1 of protocol), have measurable disease (or evaluable disease in Cohort 3), who have at least 1 post-baseline disease/tumor assessment, and have centrally confirmed FGFR amplification. Patients who discontinue due to intolerable toxicity or death prior to the first post-baseline tumor assessment will also be considered evaluable and will be classified as non-responders
- **Pharmacodynamic Population:** All patients in the All Treated Population who have evaluable pharmacodynamic biomarker data.

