5.2. Definition of a Dose-Limiting Toxicity (Cohort 4 Only)

For patients in the safety lead-in portion of Cohort 4 only, a DLT is defined as any AE that is not clearly attributable to an extraneous cause, such as an underlying disease, occurring in Cycle 1 and meeting at least one of the following criteria (Table 3).

Table 3: Dose Limiting Toxicity Definition

	Grade 4 neutropenia lasting >7 consecutive days	
Hematologic Toxicity	Grade 4 thrombocytopenia lasting >7 consecutive days	
	≥ Grade 3 thrombocytopenia with bleeding	
	Febrile neutropenia (ANC <1000/mm³ with a single body temperature of >38.3°C [101°F] or a sustained temperature of ≥38°C [100.4°F] for more than 1 hour) requiring initiation of antibiotics	
	Grade 3 total bilirubin lasting >7 consecutive days	
	Grade 4 total bilirubin	
	Grade 3 AST and/or ALT lasting >7 consecutive days	
	Grade 4 ALT and/or AST lasting >3 consecutive days	
Henotic Toxicity ^a	For patients with liver metastases, AST or ALT $>$ 8 × ULN or AST or ALT $>$ 5 × ULN lasting \ge 14 consecutive days	
Hepatic Toxicity ^a	Hy's Law criteria - concurrent observation of the following, with no other reason found to explain the findings (such as viral hepatitis A, B, or C; preexisting or acute liver disease; or another drug capable of causing the observed liver injury):	
	• Elevated aminotransferase enzymes of >3 × ULN	
	• Alkaline phosphatase (ALP) <2 × ULN	
	• Associated with an increase in bilirubin $\ge 2 \times ULN$	
Renal Toxicity	Creatinine clearance <30 mL/min for >3 days despite optimal supportive care	
Other Non-Hematologic Toxicity	≥ Grade 3 ^b	
	Any toxicities leading to a TAS-120 Cycle 1 dose intensity of <75% and/or fulvestrant dose intensity of <100%	
Other	Inability to initiate Day 1 of Cycle 2 within 14 days of schedule due to any continuously ongoing Grade \geq 2 toxicity	
	Any death not clearly attributed to the underlying disease or extraneous causes	

Abbreviations: ALP=alkaline phosphatase; ALT=alanine aminotransferase; ANC=absolute neutrophil count; AST=aspartate aminotransferase; ULN=upper limit of normal.

- a. For any Grade 3 or 4 hepatic toxicity not resolved within 7 days to Grade 0 1 (or Grade 2 if liver metastases), an abdominal computed tomography scan should be performed to assess if it is related to disease progression.
- b. The following events will not be considered DLTs:
 - Nausea, vomiting and diarrhea (unless they persist to be Grade ≥3 for >3 consecutive days despite optimal supportive care)

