10.3. Analysis Populations

The analysis study populations in this study are defined in Table 13.

Table 13: Analysis Populations

Analysis Population	Definition	
All Enrolled Population:	All patients enrolled in this study	
All Treated Population/Full Analysis Set:	All enrolled patients who received at least 1 dose of study drug	
DLT Evaluable Set:	All patients in the All Treated Population in Cohort 4, excluding those for whom the cumulative dose of TAS-120 was <75% and/or the cumulative dose of fulvestrant was <100% for reasons other than DLTs in Cycle 1, or who received prohibited concomitant medications or therapies	
Response Evaluable Set:	All patients in the All Treated Population who meet Inclusion Criterion #4, have measurable disease (or evaluable disease in Cohort 3), who have at least 1 post-baseline disease/tumor assessment, and have centrally confirmed FGFR amplification. Patients who discontinue due to intolerable toxicity or death prior to the first post-baseline tumor assessment will also be considered evaluable and will be classified as non-responders.	
PopPK Evaluable Set:	All patients in the All Treated Population who have evaluable plasma TAS-120 concentration data for analyses	
Pharmacodynamic/Biomarker Evaluable Set:	All patients in the All Treated Population who have evaluable pharmacodynamic/biomarker data for analyses	

Abbreviations: DLT=dose-limiting toxicity.

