4. STUDY DESCRIPTION

4.1. Summary of Study Design

This is a Phase 2, open-label, non-randomized, multicenter study designed to evaluate the efficacy and safety of TAS-120 and TAS-120 + fulvestrant in adult patients with locally advanced/metastatic breast cancer harboring FGFR gene amplifications. Up to approximately 168 patients will be enrolled in this study, which will be conducted at approximately 75 sites globally.

Patients will be enrolled to 1 of 4 treatment cohorts based on diagnosis and *FGFR* gene amplification status, and will receive either single agent TAS-120 in Cohorts 1-3 or TAS-120 plus fulvestrant in Cohort 4 (Figure 1).

^{*} Total number of enrolled patients including patients enrolled in Stage 1.

Figure 1. Study design flow chart

In all cohorts, a treatment cycle is defined as 28 days. All patients will receive PO TAS-120 at a dose of 20 mg QD (continuous daily dosing). Patients in Cohort 4 only will also receive intramuscular (IM) fulvestrant 500 mg on Days 1 and 15 of Cycle 1 and Day 1 of every subsequent cycle. Pre/peri-menopausal patients in Cohort 4 are required to also have ovarian suppression with goserelin as part of standard of care, having started a gonadotropin-releasing hormone (GnRH) analogue at least 4 weeks prior to the first dose of fulvestrant.

Treatment will continue until disease progression, unacceptable toxicity, or any other of the criteria for treatment discontinuation is met. For patients who discontinue treatment for reasons other than disease progression, tumor assessments should be continued until radiologic disease progression is documented or until initiation of subsequent new anticancer therapy (whichever occurs first). Patients will be followed for survival every 12 weeks (±2 weeks) until survival events (deaths) have been reported for 75% of enrolled patients or the study is terminated early by the Sponsor.

^{**} In the safety lead-in period of Cohort 4, 6 patients will initially be treated at a TAS-120 dose of 20 mg QD, with the possibility of 6 additional patients treated at 16 mg QD if 20 mg QD is not tolerated. After the safety lead-in, additional patients will be enrolled to ensure a total of 28 patients are treated at the recommended dose (including patients treated at the recommended dose in the safety lead-in.

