Cohorts 1 and 2 will initially enroll a total of approximately 19 response-evaluable patients per cohort. If \geq 4 responses (PR or CR) are observed in a cohort, that cohort will be further expanded to a total of approximately 55 response-evaluable patients.

Cohort 3 will initially enroll a total of approximately 9 response-evaluable patients. If ≥ 3 patients experience clinical benefit (CR, or SD ≥ 24 weeks) are observed, the cohort will be further expanded to a total of approximately 24 response-evaluable patients.

Because the combination of TAS-120 and fulvestrant has not been assessed in patients, **Cohort 4** will begin with a safety lead-in period. During the safety lead-in, 3 patients will initially be enrolled and will receive TAS-120 (20 mg QD) and fulvestrant (500 mg) according to the study schedule, with safety follow-up of at least 1 cycle. Patients will be assessed for DLTs and the recommended dose of TAS-120 for this cohort will be determined as follows.

- Of the initial 3 patients, if 0/3 or 1/3 patients present with a DLT, another 3 patients will be enrolled.
 - o If 0/6 or 1/6 patients present with a DLT, the safety lead-in phase will conclude and enrollment will continue to a total of 28 patients treated with TAS-120 (20 mg QD) plus fulvestrant.
- If ≥2/3 or ≥2/6 patients present with a DLT, TAS-120 20 mg QD plus fulvestrant will be defined as a non-tolerated dose level for the combination. Subsequent patients will be treated at a dose of TAS-120 of 16 mg QD plus fulvestrant, and the sequence will be repeated. Initially, 3 patients will be enrolled:
 - o If 0/3 or 1/3 patients present with a DLT, another 3 patients will be enrolled.
 - If 0/6 or 1/6 patients present with a DLT, the safety lead-in phase will conclude and enrollment will continue to a total of 28 patients treated with TAS-120 (16 mg QD) plus fulvestrant.

If $\geq 2/3$ or $\geq 2/6$ patients present with a DLT at the dose of TAS-120 at 16 mg QD plus fulvestrant, the assessment of the combination and further enrollment to Cohort 4 will be discontinued.

The detailed study schedule is shown in Table 1.

Table 1: Schedule of Events

Written informed consent will be obtained prior to any study evaluations. Evaluations on Day 1 (D1) of a cycle should be performed within 24 hours prior to dosing, unless otherwise noted. Procedures already performed during the screening period within 96 hours prior to dosing do not need to be repeated on Cycle 1 Day 1 (C1D1).

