Sample size considerations for **Cohort 4** (primary endpoint 6-month PFS) are based on a proof-of-concept Phase 2 design, differentiating a null 6-month 25% PFS rate with a target rate of 50%. Approximately 28 patients will be treated. It has approximately 80% power to reject the null hypothesis that the true 6-month PFS rate is ≤25%, considering a 1-sided alpha (type 1 error rate) of 5%. In addition, 6-12 patients will be enrolled as a safety lead-in. The patients in the safety lead-in who are treated at the recommended Phase 2 dose will be included in the main cohort of 28 patients. Thus up to 34 patients may be enrolled for this cohort.

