6.5.2.7. Dose Limiting Toxicity (Cohort 4 only)

The number and percentage of patients with dose limiting toxicity (DLT) will be presented by different dose levels of TAS-120. The patients with DLT will also be listed.

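### The DLT Evaluable Set is not restricted to the Cohort 4 safety lead-in and the DLT table names no denominator, so the DLT percentage at the expanded dose would be diluted

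*SAP*

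**What the plan says.** **Who can have a DLT.** Protocol 5.2: "For patients in the safety lead-in portion of Cohort 4 only, a DLT is defined as any AE" that meets the listed criteria in Cycle 1.

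**Who is in the set.** Protocol Table 13 (Section 10.3) begins: "All patients in the All Treated Population in Cohort 4, excluding those for whom the cumulative dose of TAS-120 was <75" percent. SAP 5.3 uses the same base population. Neither mentions the lead-in.

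**Who is taken out.** There are two kinds of exclusion: low cumulative dose of either drug, and prohibited treatment. The wording in SAP 5.3 is "for reasons other than DLTs in Cycle 1, or who received prohibited concomitant medications or therapies", and Table 13 matches it. The DLT exception belongs to the dose clauses; the final alternative, "or who received prohibited concomitant medications or therapies", has none.

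**How DLTs are reported.** SAP 6.5.2.7: "The number and percentage of patients with dose limiting toxicity (DLT) will be presented by different dose levels of TAS-120". It adds that patients with a DLT are listed, but it gives no population. SAP 6.5 makes the All Treated Population the default for safety analyses. The one place where the SAP uses the DLT Evaluable Set by name is the disposition summary in 6.3.1, by TAS-120 dose level.

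**How the lead-in works.** SAP 4.1 starts with 3 patients and goes to 6 per dose level ("6 patients will initially be treated at a TAS-120 dose of 20 mg QD"). The rule for going on is: "If 0/6 or 1/6 patients present with a DLT, the safety lead-in phase will conclude". Under SAP 4.3, lead-in patients at the recommended dose "will be included in the main cohort of 28 patients".

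**The concern.** A DLT percentage means something only among patients in whom a DLT could be recorded. By the protocol's definition those are the lead-in patients. An expansion patient can have the same toxicity in Cycle 1 and it is not a DLT. Counting such patients adds to the denominator and can never add to the numerator.

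The second question is whether the set can lose events. The dose-intensity exclusions protect a patient whose low dose was caused by a DLT. The prohibited-treatment exclusion follows as a separate alternative without that protection and without a time limit.

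DLT evaluation in Cohort 4 is a listed secondary endpoint (Protocol Table 2, SAP 3.2.2), and the protocol says the combination has not been assessed in patients before. The DLT table is where a reader will look for its short-term tolerability.

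**Working it through.** **Inputs**

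- Lead-in size per dose level: 3, then 6 (Protocol 3.1, SAP 4.1).
- Patients at the recommended dose, lead-in patients at that dose included: 28 (Protocol 10.1, SAP 4.3).
- Cohort 4 maximum: 34 (same sections).
- Dose taken forward with 0/6 or 1/6 DLTs; not tolerated at 2 or more of 3 or of 6.

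**Step 1, the plan's own count.** 28 at the recommended dose + 6 at a non-tolerated dose = 34. This reproduces. The documents state no DLT rate.

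**Step 2, patients who cannot have a DLT.** At the recommended dose, 28 − 6 = 22 are expansion patients. They are in the DLT Evaluable Set unless its exclusions remove them, and they are in the All Treated Population. Both candidate denominators therefore carry the dilution.

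**Step 3, the reported percentage at the expanded dose.** The rate is x/n, with exact Clopper-Pearson 95% limits. By the decision rule x is 0 or 1.

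| Lead-in DLTs | Lead-in denominator | All Cohort 4 patients at that dose |
|---|---|---|
| 1 | 1/6 = 16.7% (0.4 to 64.1) | 1/28 = 3.6% (0.1 to 18.3) |
| 0 | 0/6 = 0% (upper limit 45.9%) | 0/28 = 0% (upper limit 12.3%) |

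With one DLT the percentage falls by a factor of 28/6 = 4.7. With none the estimate stays at 0%, but any interval put on it would be much too tight. The SAP does not ask for an interval here; the limits only show how much information the two denominators imply.

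**Step 4, a non-tolerated dose.** Every patient at that dose is a lead-in patient. Two DLTs in six is 2/6 = 33.3% under any of these populations, so there is no dilution.

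**Step 5, the prohibited-treatment exclusion.** This matters only if the DLT Evaluable Set is the denominator. Dropping one patient with a DLT changes the table as follows:

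- expanded dose, set as now defined: 1/28 becomes 0/27;
- expanded dose, set restricted to the lead-in but with this clause unchanged: 1/6 becomes 0/5;
- non-tolerated dose: 2/6 = 33.3% becomes 1/5 = 20.0%.

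Under the All Treated default no event is lost.

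**Step 6, who could be dropped.** Protocol 5.5.2 bars other anticancer or investigational therapy during the treatment period, and certain radiation. It lets that radiation be given after discussion with the sponsor. Section 3.2.3 ends the treatment period at the last dose. The case to consider is therefore mainly a patient with a Cycle 1 DLT who stays on treatment and receives such therapy, possibly many cycles later.

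**The case against.** The SAP never says that the DLT percentage is computed in the DLT Evaluable Set. With All Treated as the default, the claim that events are lost is conditional. This stands, and the point is worded accordingly. It does not help with the dilution, because All Treated also contains the expansion patients.

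The route to losing an event is narrow. A new anticancer drug started after the last dose falls outside the treatment period. Usual supportive care is allowed (Protocol 5.5), and interacting drugs call only for caution (5.5.1). This stands too, and the documents give no frequency for what remains.

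The several-fold understatement applies to one case, exactly one DLT at the expanded dose. The table gives the number beside the percentage and the patients are listed, so a careful reader could set the one event against six. That is true, but the printed percentage and the count of evaluable patients in the disposition table would still be wrong for their purpose.

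A reader might go further and infer that a lost DLT could reverse the dose decision, with 2/6 becoming 1/5. The documents do not support that. The rule in Protocol 3.1 and SAP 4.1 counts DLTs among 3 and 6 enrolled patients, does not refer to the set, and has no outcome out of five. Nor do the documents say whether those 3 and 6 must be DLT-evaluable.

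**Conclusion.** The definition does not fit its purpose and should be corrected. As written, one lead-in DLT at the expanded dose would be reported as about 3.6% instead of 16.7%, and up to 22 expansion patients would be counted as DLT-evaluable. This assumes a full lead-in of 6, all 28 patients treated at the recommended dose, and DLTs recorded in lead-in patients only, as Protocol 5.2 implies. Dose-related exclusions could bring the set's denominator somewhat below 28. A dose declared non-tolerated is not affected.

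The missing DLT exception and the missing Cycle 1 limit are a second, conditional defect. They remove an event from the table only if this set is the denominator, and the event would remain in the listing. No primary endpoint, hypothesis test or sample size depends on the set. The consequence shown is for the reporting of a secondary safety endpoint, not for the lead-in dose decision.

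**What to change.** In Protocol Table 13 and SAP 5.3:

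- restrict the DLT Evaluable Set to Cohort 4 safety lead-in patients;
- limit the prohibited-treatment exclusion to Cycle 1;
- state that a patient with a DLT is always evaluable, whichever exclusion would otherwise apply.

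In SAP 6.5.2.7, name this set as the denominator for the DLT percentage at each dose level. This last edit is needed: with the definition alone changed, the All Treated default would still give 1/28.

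The cost is one definition in each document and one sentence in the SAP. No new data are needed, since lead-in membership follows from the order of enrolment at each dose level.

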5.4. Timing of Analysis

The interim analysis will be performed at the time a cohort (Cohort 1, 2, 3) has the required number of patients to determine if that particular cohort should continue.

The final analysis will be performed when all patients have at least 6 months follow-up. The clinical cut-off date for the final analysis is defined as the date at which all patients either discontinue from the study or have sufficient follow-up (at least 6 months) from the first dosing date of TAS-120 of the last enrolled patient, whichever comes first.

6. STATISTICAL ANALYSIS

6.1. General Methods

All recorded data will be presented in listings.

The categorical data will be summarized using frequency counts and percentages of patients. The continuous data will be summarized using number of non-missing observation (n), mean, standard deviation (SD), median, minimum and maximum unless otherwise specified.

Summary tables will be presented by cohort. Data listings will be presented with patient ID and cohort.

For concomitant medications/therapy and adverse events, the cycle number is determined based on their start/onset dates. For other collected data, the cycle number is determined based on their visit dates. These data include Lab test, Physical exam, Vital signs, Height and Weight, Ophthalmological exam, ECOG, ECG, Pregnancy test, Circulating tumor DNA (ctDNA), tumor biopsies, Scheduled tumor assessment.

When there are multiple laboratory records for a scheduled visit, the one closest to the target date will be used for analysis. If there are two or more records with the same time period to the target date, the record with the latest database entry date will be used for analysis.

Time to event distribution (e.g. progression free survival, overall survival, duration of response, time to onset of AESI in a specific category, time to resolution of AESI in a specific category) will be estimated using Kaplan Meier techniques. The number of events and censorings will be reported. When appropriate, the median along with the corresponding log-log transformed 95% CI will be estimated. Rates at fixed time points will be derived from the Kaplan Meier estimate and corresponding confidence interval will be derived based on Greenwood formula for variance derivation and on log-log transformation applied on the survivor function S(t). Confidence intervals for binomial proportions, ORR, CRB, CR rate and 6-month PFS rate, will be derived using the Clopper-Pearson method.

All the analyses of efficacy, safety, and pharmacodynamics data for this study will be performed using SAS® statistical software package, Version 9.3 or a higher version.

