The exact 2-sided 95% CI based on Clopper-Pearson methodology will be derived for ORR. The null hypothesis will be rejected if at least 15 responders observed out of 55 patients. If 17 responders observed out of 55 patients, the ORR is 30.9% and the 95% exact CI is (19.1%, 44.8%).

CBR (Cohort 3) will be calculated based on the best overall response. Because patients in Cohort 3 have non-measurable disease at baseline, the overall response will be derived based on non-target lesion response and/or the emergence of new lesion(s). The exact 2-sided 95% CI based on Clopper-Pearson methodology will be derived for CBR. The null hypothesis will be rejected if at least 10 patients with clinical benefit are observed out of 24 patients in Cohort 3.

The exact 2-sided 95% CI based on Clopper-Pearson methodology will be derived for 6-month PFS rate (Cohort 4). The null hypothesis will be rejected if at least 14 patients observed to remain alive and progression free at 6 months after the start of treatment out of 28 patients who are treated at recommended dose in Cohort 4.

Table 4. Overall Response Assessment with Target/Non-target Lesion and New Lesions

Target Lesions	Non-target Lesions	New Lesions	Overall Response
CR	CR	No	CR
CR	Non-CR/Non-PD or Not all evaluated	No	PR
PR	Non-PD or Not all evaluated	No	PR
SD	Non-PD or Not all evaluated	No	SD
Not all evaluated	Non-PD	No	Not evaluable
PD	Any	Yes or No	PD
Any	PD	Yes or No	PD
Any	Any	Yes	PD

Table 5. Confirmation Rules for Overall Response of PR and CR

Earlier Response	Later Response	Confirmed Response
(to be confirmed)	(confirmation)	
CR	CR	CR
CR	Not CR or missing	SD
PR	CR or PR	PR
PR	SD or PD or missing	SD
PR	SD and then PR (only one SD in between)	PR
SD	n/a – no confirmation needed	SD
PD	n/a – no confirmation needed	PD

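### Cohort 4's 6-month PFS rate is tested by a count that cannot carry the censoring the documents prescribe, and the written cut-off of 14 of 28 has 57.5% power, not about 80%, even with no censoring

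*SAP*

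**What the plan says.** **Design (SAP 4.3; same figures in Protocol 10.1).** "Approximately 28 patients will be treated" in Cohort 4, "differentiating a null 6-month 25% PFS rate with a target rate of 50"%. "It has approximately 80% power to reject the null hypothesis", "considering a 1-sided alpha (type 1 error rate) of 5"%.

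**Methods (SAP 6.1).** "Rates at fixed time points will be derived from the Kaplan Meier estimate", with Greenwood variance and a log-log transformation. The next sentence reads: "Confidence intervals for binomial proportions, ORR, CRB, CR rate and 6-month PFS rate, will be derived using the Clopper-Pearson method".

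**Primary analysis (SAP 6.4.1).** A two-sided 95% Clopper-Pearson interval is planned for the Cohort 4 rate. The decision rule is: "The null hypothesis will be rejected if at least 14 patients observed to remain alive and progression free at 6 months", out of 28 patients treated at the recommended dose. SAP 6.4.2 gives the same interval method for this rate in Cohorts 1-3.

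**Censoring.** Protocol 5.5 (radiation for brain metastasis, therapy for bone metastasis, locoregional therapy) and 5.5.2 (otherwise prohibited radiation given in the patient's interest) say such patients are treated as censored when the primary endpoint is analysed. SAP Table 6 censors PFS for new anticancer treatment, for discontinuation without progression or death, at data cut-off, and after missed scans. No section says how a patient censored before 6 months enters the count. The only sensitivity analysis (SAP 6.4.1.1) changes the population and keeps the method.

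**The concern.** A binomial count has two states, success and failure. A patient censored at month 3 has to be scored as a failure or dropped from the 28. The first choice pulls the estimate down. The second leaves a denominator for which no cut-off is given. The protocol's censoring instruction therefore cannot be carried out with the method that the SAP names.

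Some early censoring can arise from the calendar alone. Scans come every 8 weeks, so near weeks 24 and 32, and 6 months is about week 26 (6 × 30.4375 days = 182.6 days). SAP 5.4 allows the cut-off at 6 months after the last patient's first dose. Table 6 censors a patient still on treatment without progression at the last scan, which for a late enrollee is near week 24, just short of the landmark.

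This is the only hypothesis test in Cohort 4, in an open-label single-arm setting. If the handling is settled after the data are seen, it can decide whether the combination is called active.

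**Working it through.** **Inputs.** n = 28, null 25%, target 50%, one-sided alpha 5%, stated power about 80% (SAP 4.3); rejection at 14 or more (SAP 6.4.1). The censoring probability c is an assumption, with range 0-20%. It is the chance that a patient who would be event-free at 6 months is censored before then, independently of outcome.

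**Step 1: the plan's own figure.** Alpha = P(X ≥ r), X ~ Binomial(28, 0.25). Power = P(X ≥ r), X ~ Binomial(28, 0.50).

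| Cut-off r | Alpha | Power | Lower limit of Clopper-Pearson two-sided 95% interval |
|---|---|---|---|
| 11 | 6.79% | 90.8% | 21.5% |
| 12 | 2.94% | 82.8% | 24.5% |
| 13 | 1.12% | 71.4% | 27.5% |
| 14 (SAP) | 0.38% | 57.5% | 30.6% |

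The stated power is not reproduced by the stated rule. Fourteen of 28 is exactly the 50% target, so a drug that meets the target passes only a little more than half the time. The smallest cut-off with alpha no greater than 5% is 12, and its 82.8% fits the SAP's description. At 13 of 28 the planned interval excludes 25% but the rule does not reject, so the interval and the rule can disagree.

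**Step 2: the count with censored patients scored as failures.** The success probability becomes p(1 − c). With p = 50% that is 45% at c = 10% and 40% at c = 20%, a downward bias of 5 and 10 points. Exact power:

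| c | Cut-off 14 | Cut-off 12 |
|---|---|---|
| 0% | 57.5% | 82.8% |
| 10% | 36.4% | 66.0% |
| 20% | 18.7% | 44.9% |

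**Step 3: the count with censored patients removed.** If, for illustration, 3 patients leave the denominator and the cut-off stays at 14, then P(X ≥ 14), X ~ Binomial(25, 0.50), is 34.5%.

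**Step 4: Kaplan-Meier.** Let S be the estimate at 6 months, θ = ln(−ln S), and se = √(Greenwood sum) / |ln S|. Reject if [ln(−ln 0.25) − θ] / se > 1.645, which means that the one-sided 95% lower limit exceeds 25%. Simulation with exponential PFS, independent exponential censoring and 40,000 trials per setting:

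| c | Power (true rate 50%) | Type I error (true rate 25%) |
|---|---|---|
| 0% | about 83% | about 3% |
| 10% | about 83% | about 4% |
| 20% | about 80% | about 4% |

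If the lower limit of a two-sided 95% interval were used instead (one-sided 2.5%), power would be about 69-73%.

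**Step 5: stress test for informative censoring.** True rate 25%, with a share of progressing patients censored just before progression (an assumed worst case). With about 7.5% of patients so censored, the Kaplan-Meier type I error is about 9%. With about 15% it is about 19%.

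**The case against.** **The SAP has already chosen.** A reader might infer that the SAP flatly contradicts itself on the method. It does not go that far. The Kaplan-Meier sentence in SAP 6.1 is general and does not name this endpoint, the next sentence does, and SAP 6.4.1 and 6.4.2 both use Clopper-Pearson. That also matches the endpoint definition as a proportion of patients. Nor does any section propose a Clopper-Pearson interval around a Kaplan-Meier estimate. This part stands. What remains is the clash between a count and the censoring instructions.

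**The scoring is implied.** The rule needs "at least 14 patients observed to remain alive and progression free at 6 months after the start of treatment" out of a fixed 28, so an unobserved patient is naturally a non-success. That is the plain reading, and it is conservative. But it is not stated, and it conflicts with the protocol's instruction to censor.

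**Early censoring may be rare.** SAP 5.4 requires at least 6 months of follow-up, and scans continue after early discontinuation until progression or new therapy. Both limit the problem, and no censoring rate is given, so the size of the loss in Step 2 is conditional. The 57.5% does not depend on censoring.

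**Kaplan-Meier is not a free improvement.** It is approximate at n = 28, and starting new therapy or stopping treatment may be related to imminent progression. Step 5 shows that its error rate can then rise well above 5%. This stands, and it is why the count belongs beside it as a sensitivity analysis.

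**Conclusion.** The concern holds in this form. The Cohort 4 primary analysis is a count that cannot honour the censoring set out in Protocol 5.5 and 5.5.2 and SAP Table 6, and nothing says how patients censored before 6 months are scored. Separately, the written cut-off gives exact alpha 0.38% and power 57.5%, about 22 points below the stated 80% (80 − 57.5 = 22.5).

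It would be tempting to say that censoring takes away the stated 80%. The documents do not support that, because the rule as written never had it. About 25 points (82.8 − 57.5 = 25.3) are lost by using 14 where 12 meets the 5% level. Censoring then takes power from 57.5% to about 36% at 10% and about 19% at 20%.

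The binomial figures without censoring are exact and use only the SAP's inputs. The censoring figures rest on assumed rates and on independence between censoring and outcome.

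**What to change.** In SAP 6.1 and 6.4:

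- Take the 6-month PFS rate out of the Clopper-Pearson sentences. Estimate it by Kaplan-Meier with the Greenwood log-log interval that SAP 6.1 already specifies.
- For Cohort 4, replace the count rule with rejection of the null if the one-sided 95% lower limit exceeds 25%. State the one-sided level explicitly, because the limit of a two-sided 95% interval would not give 80% power.
- As a sensitivity analysis, report the count with patients censored before 6 months scored as not progression-free, using a cut-off of 12 of 28.

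If the sponsor prefers to keep the count as primary, change the cut-off to 12, state that patients censored before 6 months are failures, reconcile this with Protocol 5.5 and 5.5.2, and restate the power for a plausible censoring rate (66% at 10%, 45% at 20%).

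The cost is SAP wording; with Kaplan-Meier as primary, no extra patients or assessments are needed. The price of Kaplan-Meier is a small-sample approximation and sensitivity to informative censoring, and the count is there to show how far either matters.
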